The figure shows 2 Dog-leg phases each with 3 randomisation sequences. In the first, 48 hospitals (clusters) are ready to recruit and these are randomised between the 3 sequences. All 3 sequences are eventually exposed to the intervention. Sequence 1 immediately receives the training intervention and data are only collected after the intervention. In sequence 2, data are collected before and after the intervention. The final sequence collects data only before the intervention. The second dogleg commences after the first when more clusters are ready to participate (this is shown as one month on the figure, but can be delayed as practicable). Indicatively, 7 dogleg phases with 48 hospitals (336 hospitals total) each will achieve the sample size required (333 clusters). The timeline for the middle sequence (sequence 2) is shown below. The event rate will be monitored by the DMOC and the sample size reviewed after 50 centres have completed the baseline recruitment.

[figure not shown]

Figure 2: Timeline for site and patient participation

Cluster randomisation

Randomisation of hospitals will be conducted in phases. Within a phase, the available hospitals will be organised into matched triplets according to hospital size (total number of hospital beds) and World Bank country income classification (low, lower middle, upper middle, high income), and whether the hospital accepts referrals from surgeons from at other hospitals of patients needing right colectomy. Within each matched triplet, each hospital will be randomised to a different sequence (three possible randomised sequences).

Co-enrolment

EAGLE permit co-enrolments into other research studies, so long as the study intervention does is not evaluating technical or perioperative interventions where anastomotic leak is the primary outcome measure. The Data Monitoring Oversight Committee (DMOC) will monitor baseline anastomotic leak rates throughout the study period.

ELIGIBILITY

Hospital inclusion criteria

Any hospital or surgical unit performing elective and/or emergency colorectal surgery. There are no restrictions for hospital/unit size or case volume.

Patient inclusion criteria

- All adult patients (age 18 years and above) undergoing right colectomy with or without primary anastomosis. Right colectomy is defined as ileocaecal resection or right hemicolectomy (any colonic transection with the distal resection margin proximal to the splenic flexure).

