All patients, including those who did not have a primary anastomosis, will be followed-up to a maximum of 30-days postoperatively (with Day 0 being the day of surgery) by a review of their inpatient health records, routine clinic visit letters, and reports for postoperative radiological investigations arranged as part of normal patient care. There will be no additional patient contact (telephone or in-person) beyond what is normal clinical practice at each centre. The study is designed efficiently so that existing patient follow-up pathways and health records can be used, with only data that is routinely collected as part of normal clinical care being captured.

Most anastomotic leaks following ileocolic anastomosis occur in the early post-operative period (days 4-14). Although a small number of anastomotic leaks occur beyond day 30, limiting follow-up to 30 days will ensure that the vast majority of leaks are captured.

SAMPLE SIZE

Assuming no decay in the intracluster correlation over time, our 2015 data suggest an ICC of approximately 0.05 [REF 2017]. Based on feasibility (below), we assume that each hospital provides data on 10 patients over a 2-month recruitment period (5 per hospital per month). An overall 'design effect' or sample size inflation factor for our cluster-randomised dogleg design relative to an individually randomised parallel groups design can then be calculated. Using this design effect, to detect a 30% relative risk reduction in leak rate from 8.1 to 5.6% with 80% power at the 5% significance level requires 292 clusters and 3,895 patients. In practice there will be variation in recruitment at different hospitals, which can be expected to increase the required sample size. Following a published rule of thumb, we assume that this inflates the sample size by at most 14% leading to a required sample size of 333 clusters and 4,440 patients.

PROJECTED RECRUITMENT

Data for 3,208 right colectomies was submitted by 284 centres over a 2 month period to the 2015 ESCP Right Hemicolectomy Audit; an average of 11.3 patients per 2 months. 81% the sites recruited >10 patients over the 2-month period. A mean of 10 patients per centre is required for each 2 month recruitment period.

Patients per centre (2 months)	Proportion of centres
1-5	19% (n=53)
6-10	37% (n=104)

11-15	22% (n=63)
16-20	14% (n=39)
21-30	6% (n=17)
31+	3% (n=8)

Table 1: Patient recruitment data from 2015 ESCP Right Colectomy & Ileocaecal Resection Audit

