STATISTICAL ANALYSIS PLAN

This will be conducted on an intention-to-treat basis i.e. all patients recorded in the database during the scheduled 2-month recruitment periods will be included, and those in the second period will be considered exposed to the intervention regardless of whether learning from the intervention was actually implemented. The primary outcome will be 30-day anastomotic leak rate. In the primary analysis, 30-day leak rate will be modelled using mixed effects logistic regression with random cluster (hospital) effects allowing inclusion of baseline risk factors such as co-morbid disease and ASA score and adjustment for a fixed time effect between time periods.

Planned additional analyses

Pre-planned exploratory sub-group analyses of the primary outcome will be performed in the following groups:

At cluster (hospital) level:

- Number of beds (<500 versus ≥500 total hospital beds).
- Right colectomy volume (<10 patients versus ≥10 patients per 2 month period).
- Early adoption (early versus late study entrants).
- Health service expenditure per capita in purchasing parity (top versus middle versus bottom tertile).
- Proportion of operating surgeons in each centre completing the online training modules prior to 'post-implementation' data collection (high [≥80%], intermediate [50-79%], low [<50%]).
- World Bank income group (high versus middle/low income country).

At patient level:

- Indication for surgery (malignant versus benign, e.g. inflammatory bowel disease).
- Procedure urgency (elective versus expedited/ emergency).
- Age (≤65 years versus >65 years).
- Operative approach (open versus laparoscopic/ robotic).
- Anastomotic technique (stapled versus handsewn anastomosis).
- Primary operating surgeon experience as reported (trainee versus consultant).
- Primary operating surgeon specialism as reported (general versus colorectal surgeon).

Reverse analysis will also be undertaken to explore what are the characteristics of hospitals with a big change versus no change, and do these differ in respect of cluster characteristics.

DATA HANDLING AND RECORD KEEPING

Source Data

Source data within the EAGLE study will be kept as part of the participants' medical notes generated and maintained at site. As all data collected and analysed within the EAGLE study are routinely collected, source data will only be within the medical notes.

Data Management

Information will be collected at the following times:

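### The intention-to-treat rule that codes the second period as exposed fits only sequence 2 of the dog-leg; exposure should be defined by randomised sequence and scheduled period

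*Protocol*

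**What the plan says.** The protocol's Statistical Analysis Plan section sets the exposure rule for the intention-to-treat analysis: "those in the second period will be considered exposed to the intervention regardless of whether learning from the intervention was actually implemented". The same paragraph specifies a mixed effects logistic model with random hospital effects and "adjustment for a fixed time effect between time periods".

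The text to Figure 1, under Study Design, describes who contributes what:

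- Sequence 1: "Sequence 1 immediately receives the training intervention and data are only collected after the intervention".
- Sequence 2: "In sequence 2, data are collected before and after the intervention".
- Sequence 3: "The final sequence collects data only before the intervention".

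Under Cluster randomisation, hospitals are matched in triplets and the three members of each triplet go to different sequences, so allocation is 1:1:1.

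**The concern.** The rule assigns exposure by period. That works for a hospital with an unexposed first period and an exposed second one, and only sequence 2 is like that. Sequence 1 has one recruitment period and is wholly exposed; sequence 3 has one recruitment period and is wholly unexposed. The sentence reads as if written for a before-and-after study.

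This sentence is the analysis section's definition of the treatment variable for the primary outcome. If it is applied as written, the randomised comparison between sequences can be miscoded, or exposure can become the same variable as the time effect that the model must adjust for.

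**Working it through.** **Inputs.** From the protocol's Sample Size section: leak rates 8.1% and 5.6%, 80% power, 5% significance (taken as two-sided; the text does not say), ICC 0.05 without decay, *m* = 10 patients per hospital per 2-month period, 292 clusters and 3,895 patients before inflation, 333 and 4,440 after. From Study Design: the data that each sequence contributes.

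**Layout (assumption).** Figure 1 was not available. I place sequence 1 and the before-data of sequence 2 in calendar period 1, and the after-data of sequence 2 and sequence 3 in period 2. Each triplet then has four cells of 10 patients.

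**Does this layout reproduce the plan's figure?**

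- Individually randomised size per arm: n = [1.96 √(2p̄(1−p̄)) + 0.84 √(p₁(1−p₁) + p₂(1−p₂))]² / (p₁−p₂)², with p₁ = 0.081, p₂ = 0.056, p̄ = 0.0685. This gives 1,602 per arm, 3,204 in total.
- Variance of a cell mean, in units of one patient's variance: V = 0.05 + 0.95/10 = 0.145. Covariance of the two sequence 2 cells: C = 0.05. Correlation r = C/V = 0.345.
- Design effect: [1 + (m−1)ICC] × (1 − r/2) = 1.45 × 0.828 = 1.20.
- N = 3,204 × 1.20 = 3,845 patients; 3,845 / (40/3) = 288 clusters. The stated figures are 3,895 and 292, so the patient total differs by 50/3,895, about 1.3%.
- Four cells per triplet: 292 × 40/3 = 3,893. Inflation: 3,895 × 1.14 = 4,440 and 292 × 1.14 = 333.

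The layout is therefore consistent with the stated sample size. At full size there are 333/3 = 111 hospitals per sequence and 1,110 patients per cell.

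**Coding under each reading.**

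| Cell | Calendar period (assumed) | Truly exposed | Rule by calendar period | Rule by own second period, all others unexposed |
|---|---|---|---|---|
| Sequence 1 | 1 | yes | no | no |
| Sequence 2, before | 1 | no | no | no |
| Sequence 2, after | 2 | yes | yes | yes |
| Sequence 3 | 2 | no | yes | no |

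The results below are generalised least squares on the four cell means, a linear approximation to the mixed logistic model with equal cluster sizes.

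1. **Calendar period.** Sequences 1 and 3 are miscoded: 2 × 1,110 = 2,220 of 4,440 patients. The exposure column equals the period column, so intercept, time and exposure have rank 2 of 3 and the effect cannot be estimated. This identity holds wherever sequences 1 and 3 are placed in time. If the time effect is dropped, the sequence 2 contrast gets weight a = V/(2V − C) = 0.145/0.240 = 0.604, and the contrast between sequences 3 and 1 gets the rest. The estimate is a − (1 − a) = 0.208 of the true effect, so 2.5 points becomes about 0.5.

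2. **Hospital's own second period, everyone else unexposed.** Sequence 1 alone is miscoded (1,110 patients).
   - If time is also the hospital's own period, exposure again equals time: rank 2 of 3.
   - If time is calendar period, the model can be fitted. The estimator is (S2 after − S3) + (C/2V)(S1 − S2 before), with C/2V = 0.05/0.29 = 0.172. Both differences truly equal the effect, so it returns 1.172 of it, about 2.9 points instead of 2.5. Its variance is 2V − C²/(2V) = 0.290 − 0.009 = 0.281.

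3. **Exposure by sequence and scheduled period, calendar time separate.** Exposure is (1, 0, 1, 0) and time (0, 0, 1, 1) over the four cells, so the rank is 3. The estimator is ½(S1 − S2 before) + ½(S2 after − S3), which recovers 100% of the effect. Its variance is V − C/2 = 0.120, which corresponds to the design effect of 1.20. Against this, the variance of 0.281 in reading 2 is 0.281/0.120 = 2.3 times as large.

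**The case against.** The strongest reply is that the intended coding can be worked out. If second period is taken as the post-implementation period, and time as calendar period, exposure and time are not collinear and the model is the one the sample size assumes. The rest of the protocol points that way: Study Design says which sequences are exposed, Intervention timing ties the start of the intervention to the randomised sequence, and Blinding derives before-and-after status from sequence. The sentence may be meant chiefly to say that failure to implement does not move a patient out of the exposed group. It also does not say that only second-period patients are exposed. Under most literal readings the model would fail visibly at fitting, so silent bias is unlikely there. A separate SAP, not available here, may give the right coding.

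Much of this stands. A reader might infer that no reading of the sentence yields a valid treatment contrast; the documents do not support that, because the post-implementation reading with calendar time does. A reader might also infer that two of the three sequences are always miscoded. That is true only on the calendar reading; on the own-period reading sequence 3 is correctly unexposed. Finally, averaging the cells suggests that the effect vanishes on the calendar reading (6.85% in both groups) or shrinks to 7.3% versus 5.6% on the own-period reading. Those crude averages ignore the hospital effect and the time adjustment, and the planned model would not produce them.

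The contradiction remains. The protocol does not leave coding to the SAP: it states a rule, and the rule does not fit its own design. The valid reading needs two definitions that the text does not give, one for second period and one for time. If time is also taken as before versus after, the collinearity returns. One literal combination, own second period with calendar time, would run without warning.

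**Conclusion.** The concern holds as an error in the stated exposure definition, not as a flaw in the design. As written, the rule is correct for sequence 2 only. Its consequence depends on the reading: an inestimable effect, about 21% of the effect if the time term is dropped, or about 117% of the effect with 2.3 times the variance. The likely intent gives a valid analysis at the planned efficiency.

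The misclassification counts and percentages rest on the assumed placement of sequences 1 and 3, on 10 patients in every hospital-period, on an ICC of 0.05 without decay, and on a linear approximation to the logistic model. The mismatch between the rule and sequences 1 and 3 rests on none of these; it follows from the protocol's own text.

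**What to change.** Replace the sentence in the protocol's Statistical Analysis Plan section, and align any separate SAP, with wording such as:

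> Exposed = all patients in sequence 1 and post-implementation patients in sequence 2; unexposed = pre-implementation patients in sequence 2 and all patients in sequence 3, classified by randomised sequence and scheduled period regardless of actual implementation. The time effect is calendar period within the dog-leg, entered separately from exposure.

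This keeps the intention-to-treat principle that the sentence was meant to protect. It costs one sentence, leaves the sample size unchanged, and alters nothing in randomisation, data collection or conduct. It should be in place before the analysis, particularly because the Blinding section has the analysts working without knowledge of sequence, so they depend on a correct pre-specified exposure variable.

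### The primary model and the sample size both assume no decay in hospital correlation between the two periods; a hospital-by-period random effect would protect the type I error at little cost

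*Protocol*

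**What the plan says.** Protocol, STATISTICAL ANALYSIS PLAN: "30-day leak rate will be modelled using mixed effects logistic regression with random cluster (hospital) effects", with adjustment for baseline risk factors and for a fixed time effect. No hospital-by-period effect, robust variance or sensitivity analysis for decay is named.

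Protocol, SAMPLE SIZE: "Assuming no decay in the intracluster correlation over time, our 2015 data suggest an ICC of approximately 0.05". It continues: "we assume that each hospital provides data on 10 patients over a 2-month recruitment period"; the calculation is "to detect a 30% relative risk reduction in leak rate from 8.1 to 5.6"%, which "with 80% power at the 5% significance level requires 292 clusters and 3,895 patients"; and for unequal recruitment "we assume that this inflates the sample size by at most 14% leading to a required sample size of 333 clusters and 4,440 patients". Nothing is added for decay.

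Protocol, PROJECTED RECRUITMENT, on the audit: "Data for 3,208 right colectomies was submitted by 284 centres over a 2 month period".

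Protocol, Study Design (text to Figure 1): sequence 1 gives data only after the intervention, sequence 3 only before it, and sequence 2 in both periods. The abstract adds that results from the separate dog-legs will be meta-analysed.

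**The concern.** With one random intercept per hospital, two patients of a hospital are taken to be equally correlated whether they were operated on in the same period or in different periods. Write CAC for the between-period correlation as a share of the within-period correlation; the stated model and the stated sample size both set it to 1, its most favourable value. A fixed time effect removes a shift common to all hospitals but not one that differs between hospitals.

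Only sequence 2 is seen twice, but it supplies 20 of every 40 patients in a triplet. If its hospitals drift relative to the average, the hospital-only model overstates how well they serve as their own controls. The estimate itself is not biased by this. Its standard error is too small, so a false claim of benefit on the primary outcome becomes more likely than the nominal 5%.

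**Working it through.** **Inputs.** From SAMPLE SIZE: ICC ρ = 0.05, m = 10 per hospital-period, 8.1% versus 5.6%, 80% power, 5% level (taken as two-sided), inflation of at most 14%. CAC is not in the documents; 0.8 and 0.5 are assumptions, set against the protocol's 1.

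**Design effect.** With equal cells the treatment estimate is the mean of two within-period contrasts: sequence 1 minus sequence 2 in the first period, and sequence 2 minus sequence 3 in the second. Only the covariance of the two sequence 2 means depends on CAC:

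DE = 1 + (m − 1)ρ − mρ·CAC/2 = 1 + 0.45 − 0.25·CAC = 1.45 − 0.25·CAC.

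**Reproducing the plan.** Individual randomisation needs 1,602 per arm, 3,204 in all. At CAC = 1, DE = 1.20, so 3,204 × 1.20 = 3,845 patients; at 40/3 patients per hospital that is 288 hospitals. The protocol gives 3,895 and 292, a difference of 1.3%. Then 3,895 × 1.14 = 4,440 and 4,440 × 3/40 = 333. The stated size therefore corresponds to CAC = 1.

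**Standard error of the hospital-only model (linear approximation, equal sizes).** This model estimates one common correlation ρ*, roughly the average over all same-hospital pairs. A triplet has 4 × 45 = 180 within-period pairs and 10 × 10 = 100 between-period pairs, so ρ* = 0.05 × (180 + 100·CAC)/280. The model takes the design effect as 1 + 9ρ* − 5ρ* = 1 + 4ρ*.

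| CAC | ρ* | model: 1 + 4ρ* | true DE | model SE / true SE | type I error = 2Φ(−1.96 × ratio) |
|---|---|---|---|---|---|
| 1 | 0.0500 | 1.200 | 1.200 | 1.000 | 5.0% |
| 0.8 | 0.0464 | 1.186 | 1.250 | 0.974 | 5.6% |
| 0.5 | 0.0411 | 1.164 | 1.325 | 0.937 | 6.6% |

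With hospital sizes spread as in Table 1 (top band assumed 31–45, rescaled to mean 10), the same approximation gives SE ratios of 0.966 and 0.919 and type I errors of 5.8% and 7.2%.

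**Simulation of the planned logistic model**, fitted to all hospitals at once under no effect (Monte Carlo error about 0.5 points):

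| Set-up | CAC 1 | CAC 0.8 | CAC 0.5 |
|---|---|---|---|
| 112 triplets, size CV about 0.6, 2,000 runs | 5.3% | 5.5% | 6.5% |
| 333 hospitals, equal sizes, 2,000 runs | 4.1% | 6.8% | 7.1% |
| 333 hospitals, Table 1 sizes, 2,000 runs | 5.1% | 7.7% | 7.0% |
| 112 triplets, gamma-Poisson sizes, 2,400 runs | 4.2% | 5.8% | 6.0% |

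Single cells scatter and are not always monotone, but every set-up is higher with decay than without.

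**With the nested term.** A logistic simulation with fallback to hospital-only gave 3.8%, 5.0% and 4.5% at CAC 1, 0.8 and 0.5. A linear mixed model gave 5.1%, 5.3% and 5.4%, with no loss of precision at CAC 1. In the logistic fits the added variance was estimated as about zero in 57% of runs at CAC 1 and 27% at 0.8.

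**Power of a valid analysis at 4,440 patients.** If varying cluster size uses the whole 14%, 3,895 patients remain effective. Per arm, n = 3,895/(2·DE) = 1,623, 1,558 and 1,470. With SE = √[(0.081 × 0.919 + 0.056 × 0.944)/n] and power = Φ(0.025/SE − 1.96), this gives 80.6%, 79.0% and 76.6% at CAC 1, 0.8 and 0.5. Under the Table 1 spread, size variation costs about 6% rather than 14%, and power is 83.4%, 81.4% and 78.8%. With equal sizes it is 85.4%, 83.9% and 81.8%.

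**The case against.** The strongest reply is that this is detail for a statistical analysis plan that is not shown. The protocol gives its model in one sentence, which does not strictly exclude a nested term, and it declares the no-decay assumption openly. That stands in part. But the protocol does state a method, its natural reading is one intercept per hospital, and that matches the no-decay sample size, so naming the term is a concrete improvement.

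Four stronger readings are tempting, and the documents do not support them.

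- A reader might infer that 80% power is not reached. The 14% is an upper bound, and any unused part can keep power at or above 80% under mild decay.
- A reader might infer that hospital leak levels are assumed identical in both periods. A time effect is fitted, so only each hospital's deviation from the average is held constant.
- A reader might infer that the audit is cited as evidence for no decay. It is cited for the ICC value, conditional on that assumption.
- A reader might infer that the protocol expects decay because it plans to examine the "characteristics of hospitals with a big change versus no change". That exploratory analysis is most naturally about differing response to the intervention. It does not say that background correlation decays, and the type I errors above are for no effect.

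It is also fair that the gap between periods appears short (a one-month implementation period), that nothing in the documents points to a CAC as low as 0.5, and that the simulations fit all hospitals together whereas the abstract plans a meta-analysis by dog-leg.

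**Conclusion.** The point holds as a modest weakness with a cheap remedy. If the hospital correlation decays between periods, the primary model as stated gives a standard error about 2–7% too small (about 8% at CAC 0.5 with the Table 1 spread) and a type I error of roughly 5.5–7% for CAC 0.8 to 0.5; individual simulation cells reach 7.7%. If CAC is 1, nothing is wrong. Which case applies cannot be read from the documents, and a single-period audit could not have shown it.

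The consequence for power is minor: a loss of about 1 to 5 points, depending on CAC and on how much of the 14% is used. That loss shows only with a valid analysis, because too small a standard error raises nominal rejection as well.

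The figures rest on ICC 0.05, a mean of 10 patients per hospital-period, assumed CAC values, and one fit to all hospitals. Fits to single dog-legs of 48 hospitals were not examined.

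**What to change.** In STATISTICAL ANALYSIS PLAN, add to the primary model a random hospital-by-period effect nested within hospital, in each dog-leg fit if results are meta-analysed by dog-leg. State in advance that the hospital-only model is used when that variance is estimated as zero. If the statistical analysis plan already has this term, one clarifying sentence in the protocol is enough.

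In SAMPLE SIZE, add that the stated 80% power is for CAC = 1, and that it may fall to about 79% at CAC 0.8 and 77% at CAC 0.5 if varying cluster size uses the whole 14% (about 81% and 79% at the Table 1 spread, where part is unused).

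The cost is one variance term and one sentence, a slightly wider interval under decay, and frequent zero-variance fits when there is little decay, which is why the fallback must be written down beforehand. No extra hospitals or patients are needed.

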Background: Anastomotic leak is a severe, potentially life-threatening complication following right colectomy. Internationally, anastomotic leak occurs after 8% of right colectomies. Prospective cohort data demonstrate that patient selection, intraoperative factors, and technical variation are risk factors for anastomotic leak.

Aim: To assess whether implementation of the European Society of Coloproctology (ESCP) Safeanastomosis Intervention reduces risk of anastomotic leak up to 30-days following right colectomy.

Design: International, multi-centre, cluster randomised-sequence service improvement study, with the hospital as the cluster. Phased Dog-leg schedule for repeated assessments with 3 randomisation sequences. Meta-analysis of results will be performed from individual dog legs.

Eligibility: Any hospital or surgical unit performing elective and/or emergency colorectal surgery. Adults (age 18 years and above) undergoing right colectomy or ileocaecal resection for any indication are eligible, including elective, expedited or emergency surgery by open, laparoscopic or robotic approaches.

Intervention: Three-component, behavioural change intervention for surgeons, anaesthetists and operating theatre staff, supported by an online learning environment: (1) Pre-operative stratification of patients for risk of anastomotic leak; (2) Harmonisation of technique for formation and assessment of stapled and handsewn ileocolic anastomoses; (3) Implementation of a Safe-anastomosis checklist, completed in-theatre immediately prior to formation of an anastomosis and/or maturation of an ileostomy. All centres will receive the intervention.

Primary Outcome measure: 30-day overall anastomotic leak rate, defined as clinical or radiologically detected anastomotic leak or intra-abdominal or pelvic collection.

Sample size: Assuming an ICC of 0.05, and that each hospital provides data on 10 patients over a 2-month recruitment period (5 per hospital per month), 333 clusters and 4,440 participants will be required to detect an absolute risk reduction in leak rate from 8.1 to 5.6% (relative risk reduction 30%) with 80% power at the 5% significance level.

PLAIN ENGLISH SUMMARY

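### The primary model names neither the randomisation phase nor any matching factor, and the protocol does not say how it relates to the planned meta-analysis of dog-legs

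*Protocol*

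**What the plan says.** **Randomisation.** Under Cluster randomisation the protocol states: "Randomisation of hospitals will be conducted in phases". Within a phase, hospitals are formed into "matched triplets according to hospital size (total number of hospital beds) and World Bank country income classification", and a third factor is "whether the hospital accepts referrals from surgeons from at other hospitals of patients needing right colectomy". The three hospitals of a triplet go to three different sequences. Seven phases of 48 hospitals are given as indicative.

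**Primary analysis.** The Statistical Analysis Plan section names "mixed effects logistic regression with random cluster (hospital) effects allowing inclusion of baseline risk factors such as co-morbid disease and ASA score". Time enters through one further term, the same for every dog-leg as far as the text goes. Phase, triplet, beds, income class and referral status are not in the model as described. Beds and income group appear in that section only as exploratory subgroups, and referral status does not appear there at all.

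**Combining dog-legs.** The Design paragraph of the summary says: "Meta-analysis of results will be performed from individual dog legs". It gives no weights, does not choose between fixed and random effects, and does not say whether this is the primary analysis. The analysis section does not mention a meta-analysis.

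**Sample size.** The calculation starts from "Assuming no decay in the intracluster correlation over time", an ICC of 0.05 and 10 patients per hospital per 2-month period. It arrives at 292 clusters and 3,895 patients, then 333 clusters and 4,440 patients after 14% inflation for unequal recruitment.

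**The concern.** An analysis should normally reflect the groups within which the trial randomises. Here the allocation is restricted by phase and by three hospital characteristics, and the named model uses none of them.

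- **Precision.** Matching helps the final estimate only as far as the analysis uses the matching factors. At least one is plausibly prognostic, since hospital size is one of the six inputs to the leak-risk calculator described under Intervention details.
- **Comparison within phase.** Dog-legs start at different dates. A single time effect shared by all of them assumes the same change from period 1 to period 2 everywhere. Balance protects the estimate while every triplet stays complete, but not once hospitals drop out.
- **Which estimate decides the trial.** With a model in one place and a meta-analysis in another, and a covariate list introduced only by examples, a reader cannot tell which odds ratio is the primary result. An odds ratio from a logistic model also depends on the covariates in it.

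**Working it through.** **Inputs from the protocol:** leak 8.1% versus 5.6%; 80% power; 5% significance (taken as two-sided); ICC 0.05 with no decay; m = 10 patients per hospital-period; 14% inflation; 7 phases of 48 hospitals, so 16 hospitals per sequence per phase.

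**1. Reproduce the stated sample size.**
- Individually randomised, pooled variance, no continuity correction: n per arm = [1.960 × √(2 × 0.0685 × 0.9315) + 0.8416 × √(0.081 × 0.919 + 0.056 × 0.944)]² / 0.025² = 1,602, so 3,204 in total.
- Dog-leg design effect with no decay: [1 + (m − 1)ρ] × (1 − r/2), with r = mρ / [1 + (m − 1)ρ]. For m = 10 this reduces to 1 + 4ρ, which is 1.20 at ρ = 0.05. Generalised least squares on the cluster-period means also gives 1.20.
- 3,204 × 1.20 = 3,845 patients. A triplet contributes 10 + 20 + 10 = 40 patients, or 40/3 per hospital, so this is 288 clusters. Times 1.14: 4,383 patients and 329 clusters.
- The stated figures are 3,895 and 292, then 4,440 and 333. Agreement is within 1.3%.

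The full ICC of 0.05 enters this calculation, so the plan counts on no benefit from matching.

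**2. Does omitting phase cost precision?** Linear approximation, 7 phases, 16 hospitals per sequence per phase, ICC 0.05, total variance set to 1:

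| Analysis | Variance of treatment effect |
|---|---|
| One common period effect | 0.001071 |
| Plus phase main effects | 0.001071 |
| Phase-by-period effects | 0.001071 |
| Inverse-variance pooling of 7 phase estimates | 0.001071 |

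All four equal 1.20 × 4 / 4,480, with 7 × 640 = 4,480 patients. In the balanced design, omitting phase costs nothing unless leak risk differs by phase, and including it costs nothing either.

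**3. What would the matching factors bring?** The protocol does not say how much between-hospital variance they explain, so a range is assumed. Power = Φ{2.8016 × √(1.20 / DE) − 1.960}, where 2.8016 = 1.960 + 0.8416.

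| Share explained (assumed) | ICC left | Design effect | Power |
|---|---|---|---|
| 0% | 0.05 | 1.20 | 80.0% |
| 20% | 0.04 | 1.16 | 81.3% |
| 40% | 0.03 | 1.12 | 82.6% |

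Holding the within-hospital variance at 0.95 instead of rescaling the total gives 0.95 + 5 × 0.04 = 1.15 and 0.95 + 5 × 0.03 = 1.10, and power of 81.6% and 83.3%. Either way the result is about 81-83%.

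**4. Can the model afford the extra terms?** Seven phases × 2 periods = 14 phase-period parameters. Expected leaks: 4,440 × (0.081 + 0.056) / 2 = 304.

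**The case against.** **The two statements can be read together.** The analysis section speaks of two periods, which fits a single dog-leg, and never says that one model is fitted across all of them. Fitting it in each dog-leg and then pooling would satisfy both the summary and the analysis section, and phase would then be handled by stratification. This stands: a reader might infer that two incompatible primary analyses are specified, and the protocol does not support that. What remains is that nothing says which route is meant.

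**The loss is an option forgone.** The planned 80% is intact, and the gain is one to three points on an assumed range. This also stands, and it limits the size of the point.

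**Covariates and pooling details belong in a SAP.** This stands in part. The list is open and excludes no matching factor, and a separate SAP, not seen here, may settle it. But the protocol does describe its primary model and does describe its restricted randomisation, and the first does not reflect the second.

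**Two further inferences do not hold.** A reader might expect the meta-analysis to cost much power, because a random-effects pooling of seven estimates tested on a t distribution with few degrees of freedom would do so. The protocol proposes neither, and inverse-variance pooling with a normal reference matches the one-stage model (working, step 2). A reader might also infer that a hospital intercept alone makes the test invalid. If the between-period correlation were 0.8 or 0.5 of the within-period value, the design effect would be 1.45 − 0.25 × 0.8 = 1.25 or 1.45 − 0.25 × 0.5 = 1.325. The standard error would then be up to 2% or 5% too small and the type I error up to 5.5% or 6.2%. Those decay values are assumptions, the protocol states its no-decay assumption openly, and the model is consistent with it.

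**Conclusion.** The point holds as an improvement that should be made and a statement that should be clarified. It is not an error that undermines the trial. The primary model does not reflect the phases and matching factors used in the randomisation, and its relation to the dog-leg meta-analysis is left open.

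The benefit of adjusting for the matching factors is about one to three power points at no cost in patients. It rests on their explaining 20-40% of between-hospital variance, on an ICC of 0.05 and on a linear approximation. If they explain nothing, nothing is gained.

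The case for phase-by-period terms is not precision. They keep the comparison within the randomised phase if time trends differ between dog-legs or if hospitals drop out of triplets.

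**What to change.** In the Statistical Analysis Plan section, name one primary estimator: a one-stage mixed logistic model with exposure, dog-leg-by-period fixed effects, beds, income class, referral status, a closed list of patient covariates and a random hospital effect. In the summary, label the dog-leg meta-analysis a sensitivity analysis or delete the sentence.

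A hospital-by-period random effect can be added as a sensitivity analysis. Only sequence 2 hospitals, one third of the total, inform the between-period correlation. With about 10 × 0.081 = 0.8 expected leaks per hospital-period before the intervention, the model may not converge, so it is better not made primary.

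The cost is wording, and about 14 phase-period parameters against about 300 expected leaks. The matching factors are already held, because the triplets are formed from them. The sample size does not change. The change should be fixed before any outcome data are seen by allocation.
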